Study Medication: Subjects who satisfy all inclusion and exclusion criteria will be randomized to either PIO 45 mg once daily or HCQ 400 mg once daily (2 x 200 mg tablets). Randomization will occur based on the subject's (randomly assigned) unique medical record number issued by MLK or SCFHC: *odd numbers will receive HCQ; even numbers will receive PIO.* The study is open-label. The supply of PIO will be prescribed as per usual clinical practice through the outpatient pharmacies at MLK and SCFHC (or provided by the investigators if not obtainable from SCFHC because of their internal insurance coverage policies), and compliance will be determined by pill counts and referencing dispensing records from the MLK online pharmacy database (for subjects from MLK). The supply of HCQ will be purchased from a retail pharmacy specifically for the study, and compliance will be determined by pill counts assessed by the study coordinators at each follow-up visit. Subjects will be provided with a 90-day supply at the randomization visit so as to allow for potential variations in compliance and/or scheduling of the 2-month follow-up visit. Subjects must bring their remaining supply of unused medication at the every follow-up visit, and will be provided with a sufficient amount of additional HCQ at the 2-month visit to last until their final, 4-month visit (allowing again for potential variations in compliance and/or scheduling). Although all subjects should already have experience with the principles of dietary and lifestyle modifications as part of their ongoing diabetes therapy, these concepts will be reinforced at each follow-up visit.

Follow-Up Visits (Week 8, Week 16): Subjects will be seen at the CTRC in the fasting state, vital signs, weight and height will be taken, and blood will be drawn for FPG, HbA_{1c}, CBC, electrolytes, BUN, creatinine, AST, ALT, fasting insulin, and hsCRP. For subjects from MLK,

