- Compliance with the study medication will be verified with pill counts at each follow-up visit. The need for consistent use of the study medication will be reinforced if suboptimal compliance is noted.
- Adverse events and any clinically meaningful changes in physical findings will be noted. The probability of any causal relationship between the adverse event or physical finding

and the study intervention will be judged by the investigator and if necessary, reported to the IRB.

- Hypoglycemic episodes, as defined by the presence of appropriate symptoms that are alleviated by the ingestion of carbohydrates or associated with a confirmed FPG level < 60 mg/dL, will be assessed. If necessary, subjects will be instructed on how to manage hypoglycemic reactions if they have not previously received such instructions. The frequency and timing of episodes will be noted. Possible precipitants of hypoglycemia will be reviewed and corrective measures will be advised if correctable precipitants are identified. If necessary, the subject's SU dosage may be down-titrated to alleviate any recurrent hypoglycemic episodes.

Withdrawals: Subjects may either voluntarily withdraw from the study or be withdrawn by the investigators. A subject who withdraws from the study for any reason will continue to be followed for their diabetes in their respective Diabetes Clinic after their study participation is terminated. Reasons for study withdrawal by the research team include, but are not limited to, excessive non-compliance with the study medication, repeated failure to attend scheduled visits, use of any other medications known to affect glucose or lipid control, adverse effects (including confirmed FPG ≥ 300 mg/dL or clinically significant hypoglycemia not relieved by nutritional modifications or downward titration of the SU) or any other clinical situation which, in the opinion of the investigators, may jeopardize the subject's safety.

Methodologies:

Anthropometric Measurements: Standard procedures will be followed for the measurement of vital signs, weight, height, and calculated BMI.

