Laboratory Measurements: All laboratory analyses except fasting insulin and hsCRP will be obtained by the respective clinic phlebotomists specified above, and conducted by the respective clinical laboratories specified above, or the CTRC. Samples for insulin and hsCRP levels will be obtained at the CTRC, banked, and will be measured in the future by the CTRC Core Lab using commercially available RIA and/or ELISA kits: Millipore HI-14K Human Insulin RIA (Millipore, Billerica, MA); MP Biomedicals 07BC-1119 ultrasensitive CRP ELISA (MP Biochemicals, Orangeburg, NY); samples for insulin and hsCRP will remain frozen until assay reagents are available for batched runs once all samples have been collected.

Statistical Analyses:

All data will be collected onto Excel spreadsheets. Non-normal data will be log-transformed, as appropriate.

Intended Primary Endpoint: *The between-group change in the HbA_{1c} level from baseline to 4 months.*

Intended Secondary Endpoints:

A) The between-group difference in the change by 4 months of: i) % of subjects achieving HbA_{1c} $< 7.5\%$, ii) FPG, iii) weight and BMI, iv) HOMA-IR and QUICKI, and v) hsCRP and leukocyte counts;

B) For each group, the within-group change by 4 months in HbA_{1c}, FPG, weight and BMI, HOMA-IR and QUICKI, hsCRP, and leukocyte counts;

C) The between-group difference in the incidence of i) all hypoglycemic events, ii) severe hypoglycemic events, and iii) all adverse events excluding hypoglycemia.

Analysis: Changes in all continuous outcome measures will be compared between groups using 2-way repeated measures ANOVA. A chi-square analysis will be used to compare the percent of subjects achieving HbA_{1c} $< 7.5\%$ between groups. Changes within groups between baseline and

4-months will be made with one-way ANOVA. We will plan to eventually conduct both an intent-to-treat (ITT) analysis (missing data imputed using last-observation carried forward) as well as a secondary analysis of only those completed subjects with mean medication compliance $\geq 90\%$.

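### The lipid-drug withdrawal rule can end HbA1c collection by arm-aware decision in a trial with no lipid endpoint, and the gap is then filled by LOCF

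*Combined protocol and SAP*

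**What the plan says.** The Withdrawals section gives an open list of grounds, introduced by "Reasons for study withdrawal by the research team include, but are not limited to". One of them is "use of any other medications known to affect glucose or lipid control". A subject who leaves "will continue to be followed for their diabetes in their respective Diabetes Clinic after their study participation is terminated". That is routine care; nothing says that HbA1c values from it return to the trial.

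The primary endpoint is "The between-group change in the HbA_{1c} level from baseline to 4 months". The secondary between-group endpoints are the percentage below 7.5%, FPG, weight and BMI, and "iv) HOMA-IR and QUICKI, and v) hsCRP and leukocyte counts", followed by hypoglycaemia and adverse events. None is a lipid measure. The follow-up laboratory list reads "blood will be drawn for FPG, HbA_{1c}, CBC, electrolytes, BUN, creatinine, AST, ALT, fasting insulin, and hsCRP". It contains no lipid test, and neither does the screening list.

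On medication changes, Follow-Up Visits says that they are recorded and the subject counselled. Assessment Measures says that changes affecting carbohydrate or lipid metabolism are to be avoided where possible. Neither section mentions withdrawal.

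For the ITT analysis, the Analysis paragraph has "missing data imputed using last-observation carried forward". The secondary analysis is restricted to subjects who completed with mean compliance of at least 90%.

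**The concern.** A withdrawal rule that stops data collection costs outcome data. That cost needs a reason tied to what the trial measures or to safety, and the documents give none for the lipid part of this rule. The value at risk is the Week 16 HbA1c, which is the primary endpoint and could still be obtained: the visit is already scheduled and the subject remains under care in a participating clinic.

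Three features raise the stakes:

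- Treatment is open-label and withdrawal is at the investigators' discretion, so the choice of whose data stop is made knowing the arm.
- The stated aim is preliminary evidence on eventual non-inferiority. Imputation that pulls the arms together is not conservative for that aim.
- Enrolment is capped by funding at 60, which the protocol says is below its intended power.

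**Working it through.** The plan states no figure to reproduce: it gives no withdrawal rate, standard deviation or non-inferiority margin. The check is first textual, then illustrative.

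**Step 1: compare the sections on the same event.** Suppose a subject starts a drug that affects lipids.

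- Follow-Up Visits: log it and counsel the subject.
- Assessment Measures: try to avoid it.
- Withdrawals: it is a ground for ending participation.

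The protocol does not say which response applies when. Read literally, the withdrawal ground covers any use, including stable use at entry, yet no exclusion criterion addresses lipid-affecting drugs. The other two sections speak only of changes.

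**Step 2: trace what happens to the data.** Medication review is scheduled at Weeks 0, 8 and 16, the same visits as HbA1c.

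- Found at Week 16: HbA1c is due at that visit and need not be lost.
- Found at Week 8 and withdrawn: the Week 8 value is carried forward.
- Found and acted on before Week 8: baseline is carried forward, so the imputed change is zero.

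In the last two cases the subject is imputed in the ITT analysis and missing from the completer analysis. Neither analysis uses an observed Week 16 value.

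**Step 3: size per subject (illustration).** Inputs:

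- E = 2.0 points, the thiazolidinedione effect in the Background.
- n = 30 per arm, assumed from the cap of 60. Allocation by odd or even record number fixes no ratio.
- k = number of subjects withdrawn in the arm, not given.
- f = share of the effect present in the carried value: 0 for baseline; 0.5 or 0.75 assumed for Week 8.

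Arm mean change under LOCF = −E × [(n − k) + k·f] / n. Without withdrawals it is −2.00.

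| k | f = 0 (baseline) | f = 0.5 (Week 8) | f = 0.75 (Week 8) |
|---|---|---|---|
| 1 | −1.93 | −1.97 | −1.98 |
| 3 | −1.80 | −1.90 | −1.95 |
| 6 | −1.60 | −1.80 | −1.90 |

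Per subject, the shift is 2.0/30 = 0.067 points from baseline. From Week 8 it is 2.0 × 0.5/30 = 0.033 or 2.0 × 0.25/30 = 0.017.

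**Step 4: effect on the comparison.** If the same share d of each arm is carried from baseline, and these subjects would otherwise have responded like the rest of their arm, the observed difference is (1 − d) times the true one. A true 1.0-point difference becomes 0.95, 0.90 or 0.80 at d = 5%, 10% or 20% (assumed shares). If withdrawal is unequal between arms, the direction depends on which arm loses subjects.

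**Step 5: the responder endpoint.** Entry requires HbA1c of at least 7.5%, so a carried baseline counts as a failure on the <7.5% endpoint. At the two-thirds success rate quoted in the Background, each such pioglitazone subject lowers the expected arm percentage by (2/3)/30 = 2.2 percentage points.

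**The case against.** The strongest reply is that the rule is permissive. Investigators may withdraw a subject; they need not. Read with the other sections, the plan may intend to avoid, log and counsel, with withdrawal in reserve. That stands: the rule can lose data but does not have to, and the count could be zero. Discretion does not remove the problem, however, because it is exercised knowing the arm.

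Second, the visit schedule limits the loss. Medication review coincides with the HbA1c visits, so carrying baseline forward should not be the typical case. That also stands, and it is why the Week 8 columns are shown.

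Third, the issue is wider than lipid drugs. Every ground for withdrawal by the investigators leads to the same gap. That is right, and the fix should preferably cover them all. Consent pages are not in the public document, so any terms there on data after withdrawal cannot be checked.

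Four stronger readings are tempting but not supported:

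- *The lipid rule protects nothing that the trial measures.* A lipid-affecting drug might influence a secondary measure such as hsCRP. The protocol does not offer that reason, and it would not justify losing the primary HbA1c, but the absolute claim is not shown.
- *LOCF understates an effect still developing after Week 8.* The documents give no HbA1c time course for either drug. The one hydroxychloroquine time course cited concerns insulin sensitivity in non-diabetic subjects, which rose at 6 weeks and was back at baseline by 12.
- *The standard error rises by 1/√(1 − loss).* That formula describes subjects who are dropped, as in the completer analysis. LOCF keeps them in the ITT count, so the harm there is bias.
- *The withdrawal list contradicts the endpoint list.* Withdrawal grounds need not match endpoints one for one. The inconsistency is between the Withdrawals section and the sections on medication changes.

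**Conclusion.** The concern holds at modest size. As written, the plan allows investigators who know the arm to end participation over a lipid-affecting drug, with no lipid endpoint or assay and no stated rationale, while other sections treat medication changes by logging and counselling. It describes no HbA1c collection afterwards, so an obtainable primary-endpoint value can be replaced by LOCF in one analysis and be absent from the other.

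The size cannot be established because the frequency is not given. The figure of 0.067 points per pioglitazone subject rests on 30 per arm, the quoted 2.0-point effect and carry-forward from baseline; carrying Week 8 roughly halves or quarters it under the assumed shares. The shrinkage toward similarity assumes equal shares carried from baseline in both arms. In a funding-limited pilot this does not threaten the trial, but it is worth correcting because the loss is avoidable and the correction is cheap.

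**What to change.** Reconcile the Withdrawals section with Follow-Up Visits and Assessment Measures, so that one response to a medication change is stated and it is clear whether stable use at entry counts. Which drugs are allowed, and whether study drug continues, is for the sponsor; this point takes no position on either.

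Separate that treatment decision from data collection. For subjects who meet this criterion, and preferably any criterion for withdrawal by the investigators, state that with the subject's consent:

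- the drug and its start date are logged;
- the scheduled Week 8 and Week 16 HbA1c are still obtained, at the CTRC or from clinic records;
- the observed values enter the ITT analysis in the randomised arm, with LOCF only where no value can be obtained.

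The cost is a sentence or two in the protocol and minor follow-up effort, since the visits are already scheduled. The trade-off is that the ITT estimate then includes any effect of the added drug. The report should say so and give the number of such subjects by arm.

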Hydroxychloroquine (HCQ, Plaquenil) is an anti-inflammatory agent used to treat systemic lupus erythematosus, rheumatoid arthritis, Sjorgen's Syndrome and porphyria cutanea tardus. It has been noted that patients with rheumatoid arthritis and psoriasis taking HCQ exhibited a decreased risk for developing diabetes (Wasko MC, et al. JAMA 2007; 298:187-193; Solomon DH, et al. JAMA 2011; 305:2525-2531). These findings are consistent with isolated case reports of hypoglycemia in type 2 diabetic patients on the drug (Shojania K, et al. J. Rheumatol 1999; 26:195-196), its inclusion as a possible 3rd line agent in a review of treating type 2 diabetes (Llarde A, Tuck M. Drugs Aging 1994; 4:470-491), and its effect on decreasing glycemia in patients with type 2 diabetes (Gerstein HC, et al. Diabetes Res Clin Pract 2002;55:209-219; Rakedal LR, et al. Arthritis Rheum 2010;62:3569-3573; Quatraro A, et al. Ann Intern Med 1990;112:678-681). In a more recent study, HCQ (6.5 mg/kg) given to 13 obese non-diabetic subjects for 12 weeks significantly increased insulin sensitivity (as measured by the Matsuda Insulin Sensitivity Index) at 6 weeks with a return to baseline at 12 weeks (Mercer E, et al. Arthritis Res Ther 2012).

This pilot study will compare the efficacy of HCQ and pioglitazone (PIO) in patients who have failed maximum doses of metformin plus an SU. Ultimately, if HCQ proves to be as effective as PIO, another modality of treatment will be available with a drug that has fewer side effects. Even if HCQ is not as effective but does significantly lower HbA_{1c} levels, it may represent another drug for patients in whom PIO may be contraindicated. We also plan to monitor highly sensitive C-reactive protein (hsCRP) as a marker of inflammation, and since the anti-inflammatory properties of HCQ are well established, we anticipate that hsCRP levels will decrease. If insulin sensitivity does not improve or worsens with HCQ, we would conclude that inflammation does not contribute insulin resistance. Should both insulin resistance and

inflammation be reduced, further research would be needed to determine if the two change independently of each other or if either one could contribute to the other.

Primary Outcome: To collect preliminary data as to whether HCQ may ultimately be non-inferior to PIO in lowering HbA_{1c} levels in type 2 diabetic patients failing maximum doses of metformin and SU.

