Secondary Outcomes: To collect preliminary data to eventually compare a) the percentage of patients who achieve HbA_{1c} <7.5% after receiving either HCQ or PIO for 4 months; b) the effect of PIO vs. HCQ in lowering fasting plasma glucose (FPG) and weight; and c) the effects of HCQ vs. PIO on inflammation and insulin resistance.

Research Design: A 4-month, randomized, prospective, open-label comparison trial

Subjects: Type 2 diabetic patients inadequately controlled on maximally tolerated doses of metformin plus a SU.

Recruitment: Subjects will be recruited from the Diabetes Programs at MLK and South Central Family Health Center (SCFHC). These centers serve the same large population of low-socioeconomic status and low-educational level ethnic minority patients living in the south and south-central region of Los Angeles. The diabetes clinic at MLK is staffed by the faculty of the Endocrinology Division of Charles R. Drew University of Medicine and Science, and the diabetes care providers at the SCFHC clinic were trained on the same treatment protocols by the study co-investigator. This study protocol will be reviewed by the Institutional Review Board of Charles R. Drew University prior to study initiation, and an IND application will be submitted to the FDA.

Inclusion Criteria:

- Male or female, age 18-75, inclusive
- Known type 2 diabetes (diagnosed according to 1997 ADA diagnostic criteria) receiving diabetes treatment at MLK or SCFHC
- At least 3 months of treatment with maximum tolerated doses of metformin *and* a SU, *and* inadequate glycemic control (HbA_{1c} ≥ 7.5% and < 11.0%)
- Body mass index (BMI) < 45 kg/m²
- Able to comply with all scheduled visits and requirements of the protocol

Exclusion Criteria:

- Any contraindications to the use of metformin or a SU
- Extreme hyperglycemia (FPG ≥ 300 mg/dL), symptoms of polyuria or polydipsia, or HbA_{1c} ≥ 11.0%
- Current use of insulin; history or clinical suspicion of type 1 diabetes mellitus
- Symptomatic hypoglycemia occurring at an average frequency > once per day
- Highly erratic dietary schedules, extremely food insecure households, or homelessness that may adversely affect good glycemic control, as judged by the investigators
- Occupations that involve regular operation of motor vehicles or other heavy machinery that may pose a hazard in the event of unanticipated blurred vision

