- Known history of Class III or IV heart failure, cardiac arrhythmias, severe peripheral edema, advanced osteoporosis, documented bladder malignancies, or other intolerance to PIO
- Known history of collagen vascular disorders, glucose-6-phosphate dehydrogenase deficiency, hematologic disorders, psoriasis, or any known intolerance to HCQ

- Known history of pre-proliferative or proliferative retinopathy, or any clinically significant retinal abnormalities noted on the patient's most recent (i.e., within 1 year) ophthalmologic exam; subjects who have not received their routine annual ophthalmologic surveillance for diabetic retinopathy within the past year must have their annual surveillance performed before screening
- An estimated GFR (by the Modification of Diet in Renal Disease (MDRD) formula) < 45 mL/min, or a history of nephrotic syndrome (defined as a spot urine protein-creatinine ratio of > 3500 mg per g urine creatinine)
- Subjects with active hemoglobin abnormalities that render the HbA_{1c} measurement unreliable
- History of any clinically significant hepatic, cardiovascular, infectious, dermatologic, psychiatric, or other major systemic disease that, in the opinion of the investigator, may make the use of PIO or HCQ unsafe, or otherwise make the interpretation of the data difficult.
- Female subjects of childbearing potential who are sexually active and not using a reliable form of contraception or do not agree to use a reliable form of contraception. Reliable forms of contraception include systemic contraceptives (oral, implant or injection), diaphragm with spermicide, cervical cap, IUD, or condoms with spermicide.
- Current pregnancy or lactation.
- Subjects who will likely require or initiate therapy with drugs that may interfere with glucose metabolism during the course of the study (e.g., glucocorticoids).
- Subjects who are in another investigational study or have received another investigational medication within 30 days of study entry
- Subjects who are unable or unwilling to give informed consent, comply with all components of the study protocol, attend all scheduled follow-up visits, or present other barriers that would make the implementation of the protocol unusually difficult.

Schedule of Procedures: This study will be approximately 4 months in duration. Subjects will be assessed at baseline, 2 and 4 months. All visits will include an assessment of:

- Fasting plasma glucose (FPG)
- HbA_{1c}

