as with Week 0, all samples except fasting insulin and hsCRP will be obtained by the MLK phlebotomists and results will be reviewed when available; urine will be collected and processed by the MLK laboratory for a urine pregnancy test for women of childbearing potential at each follow-up visit; fasting insulin and hsCRP samples will be obtained separately at the CTRC. For subjects from SCFHC, all samples will be obtained at the CTRC (since the distance from SCFHC to CDU makes obtaining routine lab tests at SCFHC unrealistic when visits must take place at the CTRC). Based on current clinical evidence, diabetic patients are not required to perform self-glucose monitoring in the absence of insulin use, although subjects may perform self-glucose monitoring on their own if desired. Any hypoglycemic symptoms or any other adverse experiences will be reviewed and an attempt will be made to explain their occurrence. The subject's concurrent medications will be reviewed to ensure that dosages and compliance have not changed; any changes will be logged and subjects will be appropriately counseled. The entire study will last approximately 4 months.

Visit #	1	2	3
Week	0	8	16
Consent, inclusion / exclusion criteria	X		
Review of history / physical findings	X	X	X
CBC, Chemistry, FPG, HbA _{1c} , Urine pregnancy test ^a (obtained at MLK, SCFHC or CTRC)	X	X	X
Vitals, Weight, Height	X	X	X
Fasting insulin, calculation of HOMA-IR and QUICKI, hsCRP (obtained at CTRC, banked)	X	X	X
Randomization (if all criteria met)	X		
Dispense study medication supply	X	X	
Collect unused study medication supply; pill counts		X	X
Review of hypoglycemia	X	X	X
Review of adverse events		X	X
Reinforce nutrition / lifestyle	X	X	X
Review concurrent medications	X	X	X

^a For women of childbearing potential.

Assessment Measures (performed at CTRC):

- Vital signs, height and weight will be obtained at each visit, along with a brief review of the patient's history and physical findings at week 0 to look for exclusion criteria.
- Compliance with the subject's usual nutritional and lifestyle activities will be reviewed and reinforced.
- Changes in concurrent medications will be assessed at each encounter. Every effort will be made to avoid changes in concurrent medications that may influence carbohydrate or lipid metabolism (unless down-titration of SU is required).

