Sample Size Calculations: Due to limited available funding, as of late 2015, this pilot study alone will be unable to enroll the needed number of subjects to meet the originally intended level of statistical power; available funding accommodates enrollment of up to 60 subjects. However, the partial data obtainable using the available funding will still provide preliminary information as to a) the possibility of efficacy that may at least be similar between HCQ and PIO; b) the possibility of potentially similar effects of HCQ and PIO on secondary measures such as weight, inflammation, and insulin resistance; and c) the presence or possibility of any clinically significant safety concerns with HCQ in comparison to PIO that may be relevant to the eventual clinical use of HCQ for diabetes, or the value of pursuing future funding to complete the intended full enrollment to fully meet the study objectives. This pilot study will therefore still provide valuable preliminary data that will be critical towards eventually securing additional funding to continue the study and ultimately achieve the total enrollment target so as to draw the intended conclusions.

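### The primary HbA1c comparison is an unadjusted repeated-measures ANOVA with no stated visits, term, estimate or interval; a baseline-adjusted week-16 difference with a 95% CI would serve the pilot's aim better at no cost

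*Combined protocol and SAP*

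**What the plan says.** Under Statistical Analyses, the intended primary endpoint is "The between-group change in the HbA_{1c} level from baseline to 4 months". The Analysis paragraph then gives one method for all continuous outcomes: "Changes in all continuous outcome measures will be compared between groups using 2-way repeated measures ANOVA". A chi-square test covers the proportion below 7.5%, and one-way ANOVA covers the within-group changes. The 4-month time point is attached to the within-group comparison but not to the between-group ANOVA.

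HbA1c is measured three times. Schedule of Procedures states "Subjects will be assessed at baseline, 2 and 4 months", and the row of the visit table beginning "CBC, Chemistry, FPG, HbA _{1c} , Urine pregnancy test" is marked at weeks 0, 8 and 16.

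The aim is given under Primary Outcome: "To collect preliminary data as to whether HCQ may ultimately be non-inferior to PIO in lowering" HbA1c. Sample Size Calculations adds that the pilot should inform "the possibility of efficacy that may at least be similar between HCQ and PIO", and says that "available funding accommodates enrollment of up to 60 subjects", which is fewer than the originally intended power required. No margin, alpha, SD or effect size is stated.

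**The concern.** A two-way repeated-measures ANOVA yields a group term, a time term and a group-by-time term. The reference to changes points to group-by-time, but the plan does not say so, and it does not say whether week 8 is included. These choices decide whether the test addresses the stated endpoint. In an open-label study they should not be left until the data have been seen.

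The larger issue holds whichever choice is made. The pilot is meant to indicate whether HCQ could turn out to be non-inferior to PIO and to support funding for a full trial. A p-value against no difference does not do that. With up to 60 subjects, a non-significant F is compatible with HCQ being materially worse. What a funder or the designers of the next trial need is the estimated difference and how much worse HCQ could still be, and the plan does not commit to reporting either. Baseline HbA1c, a natural covariate for week-16 HbA1c, is collected but not used as one.

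**Working it through.** The plan has no figure of its own to reproduce: 60 is a funding cap.

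**Inputs**
- From the documents: up to 60 subjects; visits at weeks 0, 8 and 16; entry HbA1c from the criterion "inadequate glycemic control (HbA_{1c} ≥ 7.5% and < 11.0"%.
- Assumed: an equal split of 30 per arm, no dropout, two-sided 5%, baseline-to-week-16 correlation r of 0.3, 0.5 or 0.7, and the SDs shown below.
- If the baseline value is the qualifying one, the entry window caps the baseline SD at (11.0 − 7.5)/2 = 1.75; an even spread gives 3.5/√12 = 1.01. Nothing in the documents bounds the week-16 SD.

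**1. Weeks 0 and 16 only.** The group-by-time F equals the square of the two-sample t on the change score. A numerical check on simulated data gave 0.03275 for both. Under this reading the test matches the endpoint.

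**2. All three visits.** Group-by-time has 2 and 116 df. Under compound symmetry its noncentrality is (n/2)·Σ(d_j − d̄)² / [SD²(1 − r)], where d_j is the between-arm gap at visit j. Take a gap at week 8 only (0, 0.8, 0), n = 30 and SD 1.25:
- d̄ = 0.267 and Σ(d_j − d̄)² = 0.427, so the numerator is 15 × 0.427 = 6.4.
- Dividing by 1.5625(1 − r) gives 5.85, 8.19 and 13.65 for r = 0.3, 0.5 and 0.7.
- The test is significant 56%, 72% and about 92% of the time, although the arms do not differ at week 16.

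**3. What an interval would show.** 95% CI half-widths at n = 30 per arm, with √(2/30) = 0.2582:
- Change score: t(0.975, 58) × √(SD₀² + SD₁₆² − 2r·SD₀·SD₁₆) × 0.2582, where t = 2.0017.
- ANCOVA: t(0.975, 57) × SD₁₆·√(1 − r²) × 0.2582, where t = 2.0025.

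| SD week 0 / week 16 | Method | r = 0.3 | r = 0.5 | r = 0.7 |
|---|---|---|---|---|
| 1.2 / 1.2 | change | 0.734 | 0.620 | 0.480 |
| 1.2 / 1.2 | ANCOVA | 0.592 | 0.537 | 0.443 |
| 1.0 / 1.3 | change | 0.714 | 0.609 | 0.482 |
| 1.0 / 1.3 | ANCOVA | 0.641 | 0.582 | 0.480 |
| 1.0 / 1.5 | change | 0.792 | 0.684 | 0.554 |
| 1.0 / 1.5 | ANCOVA | 0.740 | 0.672 | 0.554 |
| any / 2.0 | ANCOVA | 0.99 | 0.90 | 0.74 |

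The ANCOVA width depends only on the week-16 SD and r. With 24 per arm (20% loss), the ANCOVA half-width at SD 1.5 is 0.83, 0.76 and 0.62.

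**4. Gain from adjustment.** With equal SDs and r = 0.3, 0.592/0.734 = 0.81, about 19% narrower. With SDs 1.0 and 1.5 and r = 0.7, both methods give 0.554, so there is no gain.

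**5. Scale.** The Background puts the TZD effect at about 2.0 points. Half-widths of 0.44 and 0.99 are 0.44/2.0 = 22% and 0.99/2.0 = about 50% of it.

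**The case against.** A reader might infer that the planned test does not match the endpoint. The documents do not support that as a flat statement. The primary endpoint runs from baseline to 4 months, the secondary endpoints are framed by 4 months, no listed endpoint uses week 8, and the method sentence speaks of changes. A two-visit ANOVA is therefore a natural reading, and it is a valid test of the endpoint. What stands is that the visits and the term are not stated.

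A reader might also infer that the ANOVA costs power. That depends on the trajectory. At SD 1.25 and r = 0.5, a 0.8-point gap building steadily gives simulated power of 59% for the three-visit interaction, 68% for the change score and 80% for ANCOVA. If the full gap is present by week 8, the figures are 72%, 68% and 79%. With SDs 1.0/1.2/1.3, an early full gap and r = 0.5, the interaction is slightly ahead of ANCOVA (79% against 77%). The pilot claims no power in any case, so the point should not rest on this.

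Omitting the baseline covariate is lost precision, not an error, and the loss can be nil. Nor do the documents show that the resulting interval would be narrow enough: they give no margin, the 2.0-point figure is a reported fall from baseline in the clinic's own experience, and the week-16 SD is unknown.

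Finally, the plan does not forbid an interval, and one could be computed later from the same data. That is true, but it leaves visits, term and adjustment to be chosen after the data are seen, and the pilot's main output rests on no commitment.

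**Conclusion.** The concern holds as under-specification plus an available improvement. The plan does not say which visits or term answer the primary question, and it commits to no estimate with an interval. Under either reading of the ANOVA, a test of no difference does not inform the stated non-inferiority or similarity aim. That conclusion rests on no assumed number. It does not invalidate the trial.

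The size does depend on assumptions. With 30 per arm, no dropout and r of 0.3-0.7, the adjusted half-width is about 0.44-0.64 points at a week-16 SD of 1.2-1.3, 0.55-0.74 at 1.5 and 0.74-0.99 at 2.0. Dropout widens all of these. The main gain is having a prespecified interval; the extra precision from adjustment is secondary.

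**What to change.** Add to the Analysis paragraph:

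> The primary analysis is the HCQ minus PIO difference in HbA1c at week 16 from an ANCOVA adjusted for baseline HbA1c in the ITT population, reported with a two-sided 95% confidence interval; any repeated-measures ANOVA is supporting.

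If the ANOVA is kept, state which visits enter and that the group-by-time term is the one tested. Name one primary model rather than a choice of models, so that the analysis is fixed in advance.

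The cost is wording only, since baseline and week-16 HbA1c are already collected. The interval may be wide, and it should be reported as such. The change does not resolve the last-observation-carried-forward imputation in the ITT analysis or the allocation by medical record number, which need separate consideration.
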